5.7.1. Adverse Events

The number and proportion of subjects reporting TEAEs will be summarized on SAF overall during the study, during the week 60 treatment period, during the follow-up period, and during the study, separately. The TEAE search criteria is described in Section [3.2](#).

AE incidence tables will be presented by treatment group for the SAF as well as subgroups for safety. TEAE summaries will present the number (n) and percentage (%) of subjects experiencing a TEAE by SOC, HLT, and PT, sorted by decreasing frequency of SOC, HLT, and PT for the REGN 1908-1909 treatment group. Multiple occurrences of AEs of the same PT (or SOC) in the same subject will be counted only once for that PT (or SOC). For tables presenting severity of events, the worst severity will be chosen for subjects with multiple instances of the same event. The denominator for computation of percentage is the number of subjects in each treatment group for safety analysis.

An overall summary of TEAEs will be provided with number and proportion of subjects with any:

- TEAE
- Serious TEAE
- TEAE of special interest (AESI)
- Serious TEAE leading to death
- Study drug related TEAE
- TEAE leading to study treatment discontinuation

Detailed summaries of TEAEs will include:

- TEAEs
 - TEAEs by primary SOC/PT
 - TEAEs by PT
 - TEAEs by severity and by primary SOC/PT
 - TEAEs related to study drug as assessed by the investigator by primary SOC/PT
 - Severe TEAEs by SOC/PT
 - Severe TEAEs related to study drug as assessed by the investigator by SOC/PT
 - Injection site reactions by HLT/PT
- Serious TEAE
 - Serious TEAEs by primary SOC/PT
 - Serious TEAEs related to study drug as assessed by the investigator by SOC/PT
- Fatal TEAEs by primary SOC/PT
- TEAE leading to study treatment discontinuation by primary SOC/PT
- AESI by AESI category (see Section 10.4), primary SOC/HLT/PT

In order to detect any AE signals, the hazard ratio (HR) may be provided together with the corresponding 95% confidence interval (CI) for the selected adverse events during the 60-week treatment period. Hazard ratios will be calculated using a Cox model including factors of treatment group and randomization strata. For patients with events, the time to events is defined as the date of first event – the date of first dose + 1. Patients without an event will be censored at the end of study period. Graphs of cumulative incidence rate over time may be provided by treatment group for selected TEAEs leading to permanent discontinuation of study treatment.

5.7.2. Clinical Laboratory Measurements

Laboratory measurements include clinical chemistry, hematology, and urinalysis results, and will be converted to standard international units and US conventional units. Summaries of laboratory variables will include:

- Descriptive statistics of laboratory result and change from baseline by visit
- The number (n) and percentage (%) of subjects with treatment emergent PCSVs. This summary will be provided based on all patients in the SAF as well as in the subgroup of SAF, patients who did not meet the PCSV criterion at baseline.
- Shift tables based on baseline normal/abnormal and other tabular and graphical methods may be used to present the results for parameters of interest

The graph of mean change and/or percent change from baseline value for lab parameters by visit will be provided.

5.7.3. Analysis of Vital Signs

Summary of vital sign variables (pulse rate, blood pressures, respiratory rate, and temperature) will include:

- Descriptive statistics of vital sign variable and change from baseline by visit
- The number (n) and percentage (%) of subjects with treatment-emergent PCSV
- Shift tables based on baseline normal/abnormal and other tabular and graphical methods may be used to present the results for parameters of interest

The last measurement will be used in the analysis if multiple data collected at the same time point.

5.8. Analysis of Pharmacokinetic Data

Descriptive statistics of total REGN1908, total REGN1909, and total drug (REGN1908+REGN1909) concentrations in serum at each sampling timepoint will be provided. Plots of mean concentration versus nominal time may be presented. Select PK parameters may be calculated.

Exposure-response analysis for biomarkers, efficacy, and safety endpoints may be conducted as appropriate, and presented in separate reports.

5.9. Analysis of Immunogenicity Data

5.9.1. Analysis of ADA Data

The immunogenicity variables described in Section 4.8 will be summarized using descriptive statistics. Immunogenicity will be characterized per drug molecule by ADA status, ADA category and maximum titer observed in patients in the ADA analysis sets. For samples confirmed as drug specific ADA positive, but found negative at the lowest titer dilution, the lowest dilution in the titer assay is imputed.

The ADA status of each patient may be classified as one of the following:

- Positive
- Pre-existing - If the baseline sample is positive and all post baseline ADA titers are reported as < 9-fold the baseline titer value
- Negative - If all samples are found to be negative in the ADA assay.
- The ADA category of each positive patient is classified as:
- Treatment-boosted - A positive result at baseline in the ADA assay with at least one post baseline titer result \geq 9-fold the baseline titer value

- Treatment-emergent - A negative result or missing result at baseline with at least one positive post baseline result in the ADA assay. Patients that are treatment-emergent will be further categorized as follows:
 - Persistent - A positive result in the ADA assay detected in at least 2 consecutive post baseline samples separated by at least a 16-week post baseline period [based on nominal sampling time], with no ADA-negative results in-between, regardless of any missing samples
 - Transient - Not persistent or indeterminate, regardless of any missing samples
 - Indeterminate - A positive result in the ADA assay at the last collection time point only, regardless of any missing samples
- The maximum titer category of each patient is classified as:
 - Low (titer <1,000)
 - Moderate ($1,000 \leq \text{titer} \leq 10,000$)
 - High (titer >10,000)
- The following will be summarized by treatment group and ADA titer level:
 - Number (n) and percent (%) of ADA-negative patients
 - Number (n) and percent (%) of pre-existing patients
 - Number (n) and percent (%) of treatment-emergent ADA positive patients
 - Number (n) and percent (%) of persistent treatment-emergent ADA positive patients
 - Number (n) and percent (%) of indeterminate treatment-emergent ADA positive patients
 - Number (n) and percent (%) of transient treatment-emergent ADA positive patients
 - Number (n) and percent (%) of treatment-boosted ADA positive patients
- Listing of all ADA titer levels will be provided for patients with pre-existing, treatment-emergent, and treatment-boosted ADA response.

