#### 11.3.4. Immunogenicity Analysis Sets

The ADA analysis set includes all patients who received study drug and had at least 1 non-missing ADA result following the first study dose.

The NAb analysis set includes all patients who received any study drug and who are negative in the ADA assay or positive for ADA with at least 1 non-missing result in the NAb assay (patients who are ADA negative are set to negative in the NAb analysis set).

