3.4. The Immunogenicity Analysis Set

The ADA analysis set (AAS) includes all treated patients who received any amount of study drug (active or placebo [safety analysis set]) and had at least one non-missing ADA result following the first dose of study drug or placebo. The ADA analysis set is based on the actual treatment received (as treated) rather than as randomized.

The NAb analysis set (NAbAS) includes all treated patients (active or placebo) that are included in the ADA analysis set and that tested negative at all ADA sampling times or tested positive at one or more post-dose ADA sampling times and had at least one non-missing post-dose NAb result (either imputed or analysis result). Samples that tested negative for ADA are not assayed in the NAb assay and the corresponding NAb results are imputed as negative and included as such in the NAb analysis set. Patients in the NAbAS with multiple post-dose ADA results which consist of both imputed NAb-negative result(s) for ADA negative samples and only missing NAb results for all ADA-positive result(s), are set to NAb negative. Patients in the NAbAS that have at least one

post-dose positive NAb analysis result are set to NAb positive even if other NAb results are missing.

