4.8. Immunogenicity Variables

The immunogenicity variables include ADA status, titer and NAb status at nominal sampling time/visit. Serum samples for ADA will be collected at the clinic visits specified in Appendix 10.2. Samples positive in the REGN1908-1909 ADA assay will be further characterized for ADA titers. Anti-REGN1908, and anti-REGN1909 neutralizing antibodies (NAb) analysis may be performed on ADA-positive serum samples. The overall immunogenicity risk will be taken into consideration to assess the need for NAb analysis. Serum samples will be banked, if NAb analysis is to be conducted at a later time.

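### Some patients still ADA-positive at their last sample are tabulated as transient, and some ADA-positive patients without any NAb result on a positive sample are set to NAb negative

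*SAP*

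**What the plan says.** **ADA classes.** SAP 5.9.1 subdivides treatment-emergent ADA. Persistent needs positives in "at least 2 consecutive post baseline samples separated by at least a 16-week post baseline period", on nominal times and with no negative in between. The other two classes are "Indeterminate - A positive result in the ADA assay at the last collection time point only, regardless of any missing samples" and "Transient - Not persistent or indeterminate, regardless of any missing samples". The number and percentage in each class are tabulated by treatment group and titer level.

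**Sampling.** SAP 4.8 states: "Serum samples for ADA will be collected at the clinic visits specified in Appendix 10.2". That schedule, like protocol Table 3, places post-baseline ADA samples at visits 6, 10, 12, 14 and 15 (weeks 12, 36, 48, 60 and 72). There is none at week 24.

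**NAb status.** Under SAP 3.4 an ADA-positive patient enters the NAb analysis set if the patient "had at least one non-missing post-dose NAb result (either imputed or analysis result"). Imputed results are the negatives assigned to ADA-negative samples. Patients who have such imputed negatives and "only missing NAb results for all ADA-positive result(s), are set to NAb negative". Protocol 11.3.4 instead admits patients who are ADA negative or "positive for ADA with at least 1 non-missing result in the NAb assay", and sets only ADA-negative patients to negative. SAP 5.9.2 gives an ADA-positive sample negative status only when it was assayed for NAb and found negative. SAP 1.2.4 does not list the difference as a change from the protocol. NAb testing is optional in both documents (protocol 9.2.6, SAP 4.8).

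**The concern.** Immunogenicity is one of two important potential risks named in protocol 3.3.

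The three ADA classes are ordered oddly. A single positive at week 72 is indeterminate, whereas positives at both week 60 and week 72 are transient, although the second patient gives more evidence of a continuing response. No later negative exists for either.

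The NAb rule gives a patient-level negative status that rests only on samples with no ADA. The samples that could have shown neutralising activity were never resolved. Because testing is optional, such gaps are foreseeable.

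At stake are the persistent, transient and indeterminate counts, the NAb status table, and the optional exposure plots in SAP 5.10.1, which may display ADA category and NAb status.

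**Working it through.** The documents give no ADA or NAb rate, so there is no planned figure to reproduce. The check applies the rules to every possible result pattern.

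**1. Sampling gaps** (study days in the schedule of events)
- (253 − 85)/7 = 24 weeks
- (337 − 253)/7 = 12 weeks
- (421 − 337)/7 = 12 weeks
- (505 − 421)/7 = 12 weeks

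**2. Patterns.** Five samples give 2⁵ − 1 = 31 patterns with at least one positive, of which 2⁴ = 16 are positive at week 72. The SAP does not say whether the 16 weeks is the span of an unbroken positive run or the distance between two adjacent samples, so both readings were applied.

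| Reading | Patterns | Persistent | Indeterminate | Transient |
|---|---|---|---|---|
| Span of run | all 31 | 12 | 1 | 18 |
| Span of run | 16 positive at week 72 | 7 | 1 | 8 |
| Adjacent samples | all 31 | 8 | 1 | 22 |
| Adjacent samples | 16 positive at week 72 | 4 | 1 | 11 |

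**3. The 8 transient patterns under the span reading** (weeks positive)
- Unbroken week 60 and 72 run, 12 weeks long and so below 16: 60+72; 36+60+72; 12+60+72.
- Negative at week 60 and positive again at week 72: 48+72; 36+72; 36+48+72; 12+72; 12+48+72.

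The 16-week threshold explains the first three. The other five arise because indeterminate is limited to a lone last positive. Under the adjacent reading, even positives at weeks 36, 48, 60 and 72 are transient.

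**4. Missing week 72 sample.** A patient positive only at weeks 48 and 60 with no later sample has a 12-week run and two positives, so is also transient.

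**5. NAb rule on the same patterns.** If no NAb assay result existed, 30 of the 31 patterns contain an ADA-negative sample and would be set to NAb negative. The pattern positive at every sample has neither an assayed nor an imputed result and falls outside the NAb set.

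**6. Direction and illustrative size.** Let *a* be the ADA-positive share of the NAb set, *p* the share of those truly NAb positive, and *u* the share of ADA-positive patients with no NAb result on a positive sample but at least one ADA-negative sample. Take missingness as unrelated to NAb status.
- SAP rule: a·p·(1 − u)
- Untested excluded: a·p·(1 − u)/(1 − a·u)
- All tested: a·p

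The first is never larger than the other two. Assume a = 10%, p = 50%, and the whole arm of 315 in the set:

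| u | SAP rule | Untested excluded | All tested |
|---|---|---|---|
| 10% | 14.2/315 = 4.5% | 14.2/311.9 = 4.5% | 15.75/315 = 5.0% |
| 30% | 11.0/315 = 3.5% | 11.0/305.6 = 3.6% | 5.0% |
| 50% | 7.9/315 = 2.5% | 7.9/299.3 = 2.6% | 5.0% |

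Excluding the untested barely moves the percentage of the whole set. The informative denominator is ADA-positive patients with a NAb result: at u = 30%, 11.0/22.05 = 50%, the assumed truth.

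**The case against.** The strongest reply is that these are descriptive labels of limited reach. Much of it stands.

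- The listed secondary endpoint is treatment-emergent ADA incidence over weeks 0 to 72. The persistence split does not touch it.
- SAP 5.10.2 relates safety and efficacy to treatment-emergent, treatment-boosted, titer and NAb-positive categories, not to persistence. Removing untested patients from the NAb negatives leaves the NAb-positive group unchanged.
- Protocol 11.4.8 makes the split optional and promises listings by patient and time point, and SAP 5.9.1 lists titers. A positive last sample therefore stays visible.
- The SAP defines transient as a residual and nowhere says it means resolved. A reader of a summary table may still take it that way.
- SAP 5.9.2 is worded by sample. It could be argued that a patient with an ADA-negative sample has a legitimate negative. Protocol 11.3.4, however, is worded by patient and asks for a result in the assay itself.

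Several stronger inferences are tempting and not supported:

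- *Everyone positive at the last sample becomes transient.* A lone last positive is indeterminate, and 7 of 16 patterns are persistent under the span reading.
- *Half of such patients are affected, all because of 12-week sampling.* The counts are unweighted patterns, the first post-baseline gap is 24 weeks, and the threshold explains only 3 of the 8.
- *Every untested ADA-positive patient becomes NAb negative.* Those positive at every sample leave the set instead.
- *The reported NAb-positive share falls from 50% to 35%.* At u = 30%, 11.0/31.5 = 35% uses ADA-positive patients as denominator. SAP 5.9.2 uses the whole NAb set, where the same assumptions give 3.5% against 5.0%.

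**Conclusion.** Both defects hold on the text, with limited reach.

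Under either reading of the 16 weeks, some treatment-emergent patients who are positive at their last sample are tabulated as transient: 8 of 16 complete week-72-positive patterns on the span reading, 11 of 16 on the adjacent reading. The number of patients cannot be derived, because the documents give no ADA rates.

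The SAP 3.4 rule conflicts with SAP 5.9.2 and protocol 11.3.4. It can only lower the NAb-positive percentage or leave it unchanged. Its size depends on how many NAb results are missing, which is not stated. The 2.5% to 4.5% against 5.0% shown above rests wholly on assumed rates.

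The tables affected are the persistent, transient and indeterminate counts and NAb status, together with the optional exposure plots. The change is worth making because it is cheap and these tables describe a named risk.

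**What to change.** **SAP 5.9.1**
- State that the 16 weeks is the span from the first to the last positive of an unbroken run.
- Define indeterminate as not persistent with a positive last available sample.
- Define transient as not persistent with a negative last available sample.

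On complete patterns positive at week 72 this leaves 7 persistent, moves the 8 transient to indeterminate (1 + 8 = 9), and leaves 0 transient.

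**SAP 3.4**
- Delete the sentence that sets these patients to NAb negative.
- Change the entry rule as well: an ADA-positive patient needs at least one NAb assay result on an ADA-positive sample, and imputed negatives from ADA-negative samples do not qualify. Deleting the sentence alone would still let untested patients in through imputed negatives.
- Report the number of ADA-positive patients without a NAb result as not evaluable.
- Add NAb positives as a percentage of ADA-positive patients with a NAb result.

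**Cost.** SAP wording and derivation code, with no new samples or visits. Any transient and NAb-negative counts produced by the present rules would fall.

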5.9.2. Analysis of NAb Data

The absolute occurrence (n) and percent of patients (%) with NAb status in the NAb analysis set will be provided by treatment groups. The NAb status is categorized as follows:

- Negative: Samples tested negative in the ADA assay, or samples positive in the ADA assay but tested negative in the NAb assay.
- Positive: Samples tested positive in the NAb assay.

5.10. Association of Immunogenicity with Exposure, Safety and Efficacy

5.10.1. Immunogenicity and Exposure

Potential association between immunogenicity and systemic exposure to REGN1908 and REGN1909 will be explored by treatment groups. Plots of individual REGN1908 and REGN1909 concentration time profiles may be provided to examine the potential impact of ADA category, maximum titer category and NAb status on these profiles.

5.10.2. Immunogenicity and Safety and Efficacy

Potential association between immunogenicity variables and safety may be explored with a primary focus on the following safety events during the TEAE period:

- Injection site reaction (serious or severe)
- Hypersensitivity (SMQ: Hypersensitivity [Narrow]) followed by manual adjudication (same as AESI ‘Hypersensitivity’))

a) Anaphylaxis (SMQ: Anaphylactic Reaction [Narrow] and identified by an algorithmic approach) followed by manual adjudication if needed. Details for the algorithmic approach are provided in Section 10.4.

Potential association between immunogenicity variables and efficacy endpoints may be explored (e.g., scatter plot or spaghetti plot).

The safety and efficacy analyses mentioned above will be conducted using the following categories:

- ADA Positive
 - Treatment-emergent
 - Treatment-boosted
- Maximum post-baseline titer category in ADA positive patients/subjects
- NAb positive

5.11. Analysis of Biomarker Data

All biomarker analyses will be performed on the FAS using all observed data.

Descriptive statistics for the observed values and change and percent change from baseline in detectable allergen specific IgE by treatment and visit will be provided for the biomarker variables.

Baseline serum total IgE, serum cat dander sIgE, serum Fel d 1 sIgE, serum Fel d 2 sIgE, serum Fel d 4 sIgE, serum Fel d 7 sIgE, and the ratio of serum Fel d 1 sIgE/ serum cat dander sIgE will be correlated to the primary and secondary clinical efficacy endpoints using spearman’s rho test.

The percent of detectable IgE at each visit (V5 and V7) compared to baseline may also be correlated to the primary and secondary clinical efficacy endpoints using spearman’s rho test. Both the spearman correlation coefficients and p-values will be reported. Multiple linear regression models may also be used to explore these relationships, with the efficacy endpoints as dependent variables and the IgE values at baseline (log transformed if appropriate) as dependent variables.

The poly-allergen sensitization status for each study subject will be determined by the number of allergen-specific IgE values that are equal to or above 0.35kUa/L. The number of allergens that each subject was sensitized to will be correlated with the primary and secondary clinical outcomes.

5.12. Sample Size Adjustment

Once at least 50% of patients are enrolled, if the observed blinded standard deviation (SD) for CSMS during the initial 12 weeks is greater than a 5% increase over the assumed SD (6.2), sample size may be increased accordingly, see Appendix Section [10.6](#). If the SD is lower than the current assumption (6.2), then no adjustment will be made. Similar methods may be considered if the SD of TNSS is larger than a 5% increase over the assumed SD (2.3).

6. DATA CONVENTIONS

The following analysis conventions will be used in the statistical analysis.

6.1. Definition of Baseline for Efficacy/Safety Variables

Unless otherwise specified, the Baseline assessment for all measurements will be the latest available valid measurement taken prior to the first administration of study drug. If any randomized patients are not treated, the baseline will be the last value on or prior to the randomization. The following rules specify the determination of baseline by both date/time information:

- For the AE, lab, PK and ADA data, both date and time of the measurement will be used to determine baseline by comparing with the first injection date and time.
- For other data except AE, lab, PK or ADA, only date of the measurement will be used to determine baseline by comparing with the first injection date.

For the rescreened patients, all data from the same patient will be used to derive baseline regardless if the data is from the screen-failure subject ID or enrolled subject ID.

